8.2 Serious Adverse Event Definition

An SAE is any untoward medical occurrence that at any dose:

- Results in death;
- Is life-threatening (an event which places the patient at immediate risk of death from the event as it occurred. It does not include an event that had it occurred in a more severe form might have caused death);
- Requires inpatient hospitalization or prolongation of existing hospitalization;
- Results in persistent or significant disability/incapacity;
- Is a congenital anomaly or birth defect;
- An important medical event that may not be immediately life-threatening or result in death or hospitalization but may jeopardize the patient or may require intervention to prevent one of the other outcomes listed in the definition above (e.g., such events include allergic bronchospasm, blood dyscrasias or convulsions, or the development of drug dependency or abuse).

8.3 Eliciting Adverse Event Information

The patient should be asked about medically relevant changes in his/her health since the last visit. The patient should also be asked if he/she has been hospitalized, had any accidents, used any new medications, or changed concomitant medication routines (both prescription and OTC).

In addition to patient observations, AEs will be documented from any clinically relevant laboratory findings, physical examination findings, ECG changes, or other findings.

8.4 Adverse Event Reporting

The Investigator is responsible for reporting all AEs that are observed or reported after the first dose of study drug regardless of their relationship to study drug through until the end of the reporting periods defined in [Section 8.5](#). For patients who meet the criteria for Rapid Disease Progression at Month 9 and receive their last dose of study drug on Day 252 but remain on the study, AEs will be followed through Day 294. Following Day 294, only study-procedure-related AEs will be collected (e.g., skin-biopsy-related AE, venipuncture-related AE).

Any medical condition that is present when a patient is screened and does not deteriorate should not be reported as an AE. However, if it does deteriorate at any time during the study, it should be reported as an AE.

All AEs must be fully recorded in the site's source records and in the patients' CRF, whether or not they are considered to be drug-related. Each AE should be described in detail: onset time and date, description of event, severity, relationship to investigational product, action taken, and outcome (including time and date of resolution, if applicable).

Adverse events should be followed through until the end of the reporting periods defined in [Section 8.5](#) or until recovery to the normal state has been achieved, whichever occurs first. In the event of a patient not returning to the clinical unit, the outcome of this event will be recorded as lost at follow-up.

For patients who withdraw from the study early, ongoing AEs will be followed until resolution or 28 days from last dose, whichever occurs first.

8.5 Adverse Event Reporting Period

AEs and SAEs will be reported according to the following timeframes:

- For patients who complete the study, AEs will be assessed through the End of Study visit on Day 567 or the Follow-up visit on Day 602 (depending whether or not the patient plans to roll over to the open-label extension study). All AEs that occur after the start of study drug administration on Day 0 must be reported in detail on the appropriate CRF page and followed to satisfactory resolution, or through the end of study visit on Day 567 or Day 602 (depending whether or not the patient plans to roll over to the open label extension study) after the last dose of study drug administration. SAEs will be followed through the end of study visit on Day 567 or Day 602 (depending whether or not the patient plans to roll over to the open label extension study), or until satisfactory resolution, or until the SAE is considered by the Investigator to be chronic or the patient is stable, whichever occurs first.
- For patients who meet the criteria for Rapid Disease Progression at Month 9 and receive their last dose of study drug on Day 252 but remain on the study, AEs will be followed through Day 294. Following Day 294, only study-procedure-related AEs will be collected (e.g., skin-biopsy-related AE, venipuncture-related AE). SAEs will be followed by the Investigator until satisfactory resolution or the Investigator deems the SAE to be chronic or stable.

- For patients who withdraw from the study early, ongoing AEs will be followed until resolution or 28 days from last dose, whichever occurs first. SAEs will be followed by the Investigator until satisfactory resolution or the Investigator deems the SAE to be chronic or stable.

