 - h. The patient will be asked to walk 10 meters. The walk must be completed without assistance from another person; ambulatory aids such as canes and walkers are permitted. The time required for the patient to walk 10 meters will be recorded. Two assessments will be performed on separate days (1 assessment on each day). The second (repeat) assessment must be conducted at least 24 hours (approximately) after the first assessment, but not more than 7 days apart.
 - i. Grip strength will be measured using a dynamometer held in the dominant hand. Every effort will be made to use the same device for a patient throughout the duration of the study. Two assessments will be performed on separate days (1 assessment on each day). The second (repeat) assessment must be conducted at least 24 hours (approximately) after the first assessment, but not more than 7 days apart.
 - j. Vital signs to include: blood pressure, pulse rate, temperature, and respiratory rate. Parameters are to be measured in the supine position using an automated instrument after the patient has rested comfortably for 10 minutes.
 - k. All ECGs are to be obtained in triplicate.
 - l. A pregnancy test (urine- or serum-based) will be performed on all females of child-bearing potential.
 - m. Concomitant medications/treatments will be collected through Day 294 (Week 42) only. Data on subsequent FAP treatment regimens will be collected separately.
 - n. Adverse events will be collected through Day 294 (Week 42) only. See [Section 8.5](#) for SAE reporting periods.
 - o. Following the Day 294 (Week 42) visit, only adverse events that are considered related to the study procedures will be collected (e.g., skin biopsies, venipunctures).
 - p. At these time points, data will be collected through phone contact.
 - q. Study personnel will contact patients by phone to query for general health status and information on subsequent FAP treatment regimens.
 - r. INR assessment only, which is to be used for qualification visit for Study TTR02-006.

ABBREVIATIONS

Abbreviation	Definition
Σ5	5 attributes
ADA	Anti-drug antibodies
AE	Adverse event
ALT	Alanine transaminase
ANC	Absolute neutrophil count
ANCOVA	Analysis of covariance
aPTT	Activated partial thromboplastin time
AST	Aspartate transaminase
ATTR	Transthyretin-mediated amyloidosis
BUN	Blood urea nitrogen
CAS	Central Assessment Site
CC	Complete case
CFR	Code of Federal Regulations
CL _R	Renal clearance
CMAP	Compound muscle action potential

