6.2.4.1 Twenty-One-Day Follow-up Visit (End of Study)

The following procedures will be performed at the 21-Day Follow-up visit (EOS; Day 567).

- Perform a physical examination;
- Measure weight;
- Measure vital signs;
- Collect blood sample for serum TTR protein, RBP, and vitamin A. Additionally, aliquots of serum samples will be taken for long-term frozen storage, to permit testing of additional proteins related to FAP;
- Perform a pregnancy test (for females of child-bearing potential only);
- Obtain information on concomitant medications;
- Document any AEs.

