8.11 Serious Adverse Event Reporting

An assessment of the seriousness of each AE will be made by the Investigator. Any AE and laboratory abnormality that meets the above seriousness criteria (Section 8.2) must be reported immediately to the CRO, always within 24 hours from the time that site personnel first learn of the event. All SAEs must be reported regardless of the relationship to study drug.

The initial report should include at least the following information:

- Patient's study number;
- Description and date of onset of the event;
- Criterion for serious;
- Preliminary assignment of causality to study drug.

SAE reporting will be via electronic data capture (EDC).

To report the SAE, complete the SAE form electronically in the electronic data capture (EDC) system for the study. When the form is completed, [REDACTED] Safety personnel will be notified electronically and will retrieve the form. If the event meets serious criteria and it is not possible to access the EDC system, send an email to [REDACTED] [REDACTED] [REDACTED] or call the [REDACTED] SAE hotline (phone number will be provided in the Study Manual), and fax the completed back-up paper SAE form to [REDACTED] (fax number will be provided in the Study Manual) within

24 hours of awareness. When the EDC system becomes available, the SAE information must be entered into the EDC system within 24 hours of the system becoming available.

██████████ Safety personnel will be available for SAE reporting on a 24-hour basis. Incoming reports will be reviewed during normal business hours.

Within 24 hours of receipt of follow-up information, the investigator must update the SAE form electronically in the EDC system for the study and submit any supporting documentation (e.g., patient discharge summary or autopsy reports) to ██████████ Safety personnel via fax or e-mail. If it is not possible to access the EDC system, refer to the procedures outlined above for initial reporting of SAEs.

Appropriate remedial measures should be taken by the Investigator using his/her best medical judgment to treat the SAE. These measures and the patient's response to these measures should be recorded. All SAEs, regardless of relationship to study drug, will be followed by the Investigator until satisfactory resolution or the Investigator deems the SAE to be chronic or stable. Clinical, laboratory, and diagnostic measures should be employed by the Investigator as needed to adequately determine the etiology of the event.

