7. APPENDICES

7.1. Detailed Statistical Methodology for Pattern Mixture Model

In the PMM analysis, similar to the primary analysis, mNIS+7 assessments performed after the initiation of alternative treatment for FAP will be treated as missing. For non-monotone missing data, the 9-month assessment will be imputed as the treatment group mean. The non-monotone missing data is expected to be rare.

As an initial step, an intermediate mNIS+7 dataset for all mITT patients will be prepared which will include the key variables listed in the table below.

Key Variables	Description
Patient number	Unique subject ID for each patient in mITT population
Treatment arm	Placebo or patisiran
Baseline variables	Including gender, genotype, age at ATTR onset, previous tetramer stabilizer use, region, KPS, FAP stage (I vs. II/III), and cardiac subpopulation.
Baseline mNIS+7 score	
mNIS+7 total score change from baseline at Month 9	Set as missing if a patient does not have 9-month data; If a patient has 18-month mNIS+7 but is missing 9-month (non-monotone missingness), the 9-month value will imputed as the treatment group mean.
On-treatment flag for Month 9	If 9-month assessment is non-missing: If assessment date – last dose date \leq 60 days, then flag = “yes” otherwise flag = “no” If 9-month assessment is missing: If Day 254 (scheduled 9-month visit) – last dose date \leq 60, then flag = “yes” otherwise flag = “no”
mNIS+7 total score change from baseline at Month 18	Set as missing if a patient does not have 18-month data
On-treatment flag for Month 18	If 18-month assessment is non-missing: If assessment date – last dose date \leq 60 days, then flag = “yes” otherwise flag = “no” If 18-month assessment is missing: If Day 554 (scheduled 18-month visit) – last dose date \leq 60, then flag = “yes” otherwise flag = “no”
Death flag	Flag = “yes” if a patient has missing 18-month mNIS+7 and death day \leq 561; otherwise flag = “no”

Step 1: For patients who have missing data and are alive before Month 18: imputation of missing data for the placebo arm and for the patisiran arm during the on-treatment period.

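### For rapid progressors who stop study drug but stay on study, the protocol gives no reporting window for new SAEs after Day 294, and its procedure-related-only limit conflicts with the all-SAE rule in section 8.11

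*Protocol*

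**What the plan says.** The passages concern patients who meet the rapid-progression criterion, "receive their last dose of study drug on Day 252 but remain on the study" (Protocol 8.5).

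- **AE limit.** Section 8.4 says "AEs will be followed through Day 294. Following Day 294, only study-procedure-related AEs will be collected", and 8.5 repeats it: "Following Day 294, only study-procedure-related AEs will be collected". Sections 7.5.7 and 8.1 carry the same limit. In the modified visit schedule, 6.4.2 announces it, and the lists in 6.4.4 to 6.4.7 then ask only for procedure-related events.
- **Schedule table.** Table 1-3 footnote n says "Adverse events will be collected through Day 294 (Week 42) only" and then refers to section 8.5 for SAE reporting periods. Footnote o restricts later collection to procedure-related events.
- **SAE sentence in the same 8.5 bullet.** "SAEs will be followed by the Investigator until satisfactory resolution or the Investigator deems the SAE to be chronic or stable".
- **General SAE rule.** Section 8.11: "All SAEs must be reported regardless of the relationship to study drug", within 24 hours of site awareness.
- **Contacts after Day 294.** Phone calls on Days 378 and 462 about general health status and FAP treatment (6.4.3), then the Day 546 visit, the 18-month assessment and the End of Study visit on Day 567.
- **Use of deaths in the SAP.** In the pattern-mixture model (SAP 7.1) the death flag is set to yes "if a patient has missing 18-month mNIS+7 and death day" is 561 or earlier.

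**The concern.** Ending routine collection of non-serious AEs some weeks after the last dose is an understandable choice. Serious events are different, because these patients remain trial participants under blinded follow-up for about nine more months. If one part of the protocol limits collection to procedure-related events and another demands every SAE, each site has to choose which to follow. Whether a hospitalisation or death enters the safety database then depends on the site. Read literally, the limit also leaves out an SAE that the investigator suspects is related to the drug, since only a procedure relationship qualifies.

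At stake are the completeness of the SAE and death listings (SAP 4.6.2), the reporting duties in 8.11, and possibly the identification of deaths for one sensitivity analysis of the primary endpoint.

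**Working it through.** The documents give no figure for this gap, so there is none to reproduce. Days below are protocol days (first dose = Day 0) unless marked otherwise.

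**1. Can the passages be read together?**

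- Section 8.5 introduces its bullets as timeframes for both AEs and SAEs. The Day 294 limit sits in one of those bullets.
- Section 8.11 treats an SAE as an AE or laboratory abnormality that meets the seriousness criteria, so a limit on AEs reaches SAEs unless something says otherwise.
- Footnote n does separate the two and refers to 8.5. There, the only SAE sentence for this group sets how long an SAE is followed. It gives no last onset day for new SAEs, so the cross-reference does not settle the question.
- Section 8.11 has neither a time limit nor an exception for this group.
- By the definition in 4.5, a rapid progressor who returns at Month 18 has completed the study. The first 8.5 bullet would then assess AEs to Day 567 or 602, while the second stops at Day 294. The more specific bullet presumably governs, but the text does not say so.

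Take an unrelated hospitalisation reported at the Day 378 call. It must be reported under 8.11 and is outside collection under the literal second bullet of 8.5.

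**2. Length and size**

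- Gap: 567 − 294 = 273 days. Share of study follow-up: 273/567 = 48.1%.
- Share of follow-up after the last dose: 273/(567 − 252) = 273/315 = 86.7%.
- Patients: Protocol 1.4 expects fewer than 5% to meet the definition, so fewer than 0.05 × 200 = 10. Only those who then stop drug and stay on study are affected.
- Ceiling on exposure: 10 × 273/365.25 = 7.5 patient-years.

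**3. Treatment-emergent tables**

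SAP 4.6.2 counts onset through 28 days after the last dose: 252 + 28 = Day 280, which is before Day 294. A new-onset SAE in the gap would stay out of those tables even if every one were collected. The exception is the SAP's clause on conditions present at baseline that worsen, or are later judged drug-related, through the end of the study.

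**4. Death flag**

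The SAP numbers the first dose as Day 1, so its Day 561 is protocol Day 560, and 560 − 294 = 266 of the 273 gap days fall under the flag. If a death were missed:

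- *Placebo patient:* imputed as missing at random from placebo data, instead of drawn from the worst 10% of changes.
- *Patisiran patient:* last dose is SAP Day 253, and 554 − 253 = 301 days exceeds the 60-day on-treatment limit, so the value is imputed from placebo data.

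**5. Split by arm**

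The documents do not give it. As an illustration, assume a 9-month placebo mean change of 12 (half of 24), an SD of 8 to 16, and the 24-point criterion alone. With about 67 placebo and 133 patisiran patients and half of the 8.95-point design effect present, the patisiran mean is 12 − 4.475 = 7.525.

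| SD | Placebo above 24 | Patisiran above 24 | Placebo share |
|---|---|---|---|
| 8 | 4.5 | 2.6 | 63% |
| 16 | 15.1 | 20.2 | 43% |

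With a patisiran mean between 0 and −2.5 the placebo share is 63% to 99%. Only the shares are of use here. The counts ignore the FAP-stage requirement.

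**The case against.** The best defence is that SAE reporting was never meant to stop. No passage names SAEs as excluded, footnote n points away from the AE limit, the SAE sentence in 8.5 carries no day limit, and 8.11 is unqualified. This stands as a statement of likely intent. It does not supply the missing onset window, and the visit lists that sites work from mention only procedure-related events.

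A reader might go further than the text allows in four ways.

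- *That serious-event data are absent for half of follow-up.* Procedure-related SAEs and follow-up of existing SAEs continue, and calls and visits remain. Only the systematic capture of new non-procedure SAEs is in doubt.
- *That the affected patients are mainly placebo, so the by-arm safety comparison is biased.* The split is unknown. Under half the design effect it could be about even, and the treatment-emergent window closes before the gap opens.
- *That a definite number of SAEs would be lost.* Any such number needs an SAE risk that the documents do not give, and also assumes no capture at all despite 8.11.
- *That a missed death is treated as missing at random in either arm.* That holds for placebo only. Moreover, the flag uses a death day that is not tied to an AE form, deaths are likely to surface through the calls, visits and withdrawal records, and the pattern-mixture model is one of four sensitivity analyses.

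**Conclusion.** The inconsistency is real and narrow. For rapid progressors off drug but on study, the protocol does not define whether new non-procedure SAEs are collected between Day 294 and Day 567, and the literal AE limit cannot be squared with 8.11. The period is 48% of study follow-up but concerns fewer than 10 expected patients and at most about 7.5 patient-years.

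The likely consequence is capture that varies by site. It affects SAE and death listings, safety reporting and possibly the pattern-mixture death flag. The primary analysis is not affected, and the treatment-emergent tables barely are. The size rests on the protocol's own expectation of fewer than 5%; a higher rate of rapid progression would enlarge it in proportion. The conclusion does not depend on any assumed split by arm or SAE risk.

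**What to change.** Reconcile the passages with 8.11. In the rapid-progression bullet of 8.5, state that after Day 294 non-serious AEs are limited to procedure-related events, while all new SAEs and deaths are collected through the End of Study visit (Day 567), regardless of relationship. Bring 7.5.7, 8.1, 8.4, the lists in 6.4.2 to 6.4.7 and Table 1-3 footnotes n and o into line. Ask about SAEs at the existing Day 378 and Day 462 calls and at the later visits.

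No visit is added and the SAP needs no change. The cost is the protocol wording and a few extra SAE forms.

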8.6 Assessment of Causality

Causal relationship assessment to drug treatments is required for purposes of reporting AEs. To promote consistency, the following guidelines should be taken into consideration along with good clinical and scientific judgment when determining the relationship of drug treatments to an AE:

- Definitely Related:** A clinical event, including laboratory test abnormality, occurring in a plausible time relationship to the medication administration, and which cannot be explained by concurrent disease or other drugs or chemicals. The response to withdrawal of the drug should be clinically plausible.
- Possibly Related:** A clinical event, including laboratory test abnormality, with a reasonable time sequence to the medication administration, but which could also be explained by concurrent disease or other drugs or chemicals. Information on the drug withdrawal may be lacking or unclear.
- Unlikely Related:** A clinical event, including laboratory test abnormality, with little or no temporal relationship to medication administration, and which other drugs, chemicals, or underlying disease provide plausible explanations.
- Not Related:** A clinical event, including laboratory test abnormality, that has no temporal relationship to the medication or has more likely alternative etiology.

8.7 Assessment of Severity

Adverse events are to be graded according to the categories detailed below.

- Mild:** Mild events are those which are easily tolerated with no disruption of normal daily activity.
- Moderate:** Moderate events are those which cause sufficient discomfort to interfere with daily activity.
- Severe:** Severe events are those which incapacitate and prevent usual activity.

Changes in severity should be documented in the medical record to allow assessment of the duration of the event at each level of severity. Adverse events characterized as intermittent require documentation of the start and stop of each incidence. When changes

in the severity of an AE occur more frequently than once a day, the maximum severity for the experience that day should be noted. If the severity category changes over a number of days, then those changes should be recorded separately (with distinct onset dates).

8.8 Action Taken for Adverse Event

Action taken in regards to study drug will be defined as:

- None;
- Infusion interrupted and restarted at a later time;
- Infusion stopped and was not restarted at a later time;
- Infusion cycle delayed.

8.9 Outcome of Adverse Event

Outcome will be defined as:

- Resolved (with or without sequelae);
- Ongoing;
- Lost to follow-up.

8.10 Coding of Adverse Events

The Medical Dictionary for Regulatory Activities (MedDRA[®]) will be used to code AEs.

8.11 Serious Adverse Event Reporting

An assessment of the seriousness of each AE will be made by the Investigator. Any AE and laboratory abnormality that meets the above seriousness criteria (Section 8.2) must be reported immediately to the CRO, always within 24 hours from the time that site personnel first learn of the event. All SAEs must be reported regardless of the relationship to study drug.

The initial report should include at least the following information:

- Patient's study number;
- Description and date of onset of the event;
- Criterion for serious;
- Preliminary assignment of causality to study drug.

SAE reporting will be via electronic data capture (EDC).

To report the SAE, complete the SAE form electronically in the electronic data capture (EDC) system for the study. When the form is completed, [REDACTED] Safety personnel will be notified electronically and will retrieve the form. If the event meets serious criteria and it is not possible to access the EDC system, send an email to [REDACTED] [REDACTED] [REDACTED] or call the [REDACTED] SAE hotline (phone number will be provided in the Study Manual), and fax the completed back-up paper SAE form to [REDACTED] (fax number will be provided in the Study Manual) within

24 hours of awareness. When the EDC system becomes available, the SAE information must be entered into the EDC system within 24 hours of the system becoming available.

██████████ Safety personnel will be available for SAE reporting on a 24-hour basis. Incoming reports will be reviewed during normal business hours.

Within 24 hours of receipt of follow-up information, the investigator must update the SAE form electronically in the EDC system for the study and submit any supporting documentation (e.g., patient discharge summary or autopsy reports) to ██████████ Safety personnel via fax or e-mail. If it is not possible to access the EDC system, refer to the procedures outlined above for initial reporting of SAEs.

Appropriate remedial measures should be taken by the Investigator using his/her best medical judgment to treat the SAE. These measures and the patient's response to these measures should be recorded. All SAEs, regardless of relationship to study drug, will be followed by the Investigator until satisfactory resolution or the Investigator deems the SAE to be chronic or stable. Clinical, laboratory, and diagnostic measures should be employed by the Investigator as needed to adequately determine the etiology of the event.

The Investigator will be responsible for reporting all SAEs to the local independent ethics committee (IEC) or Institutional Review Board (IRB) when required by national regulations.

Alnylam or its representative will be responsible for the reporting of all relevant events to the concerned regulatory authorities according to all applicable regulations.

In Europe, in accordance with the Directive 2001/20/EC, the Competent Authorities and the Ethics Committees in the concerned Member States will be notified of fatal and life-threatening Suspected Unexpected Serious Adverse Reactions (SUSARs) as soon as possible but no later than 7 calendar days after Alnylam or its representative has first knowledge of the minimum criteria for expedited reporting. Non-fatal and non-life-threatening SUSARs should be reported no later than 15 calendar days after Alnylam or its representative has first knowledge of them.

The Investigator may be informed by Alnylam or its representative of SAEs from other Investigators or clinical studies which may have relevance to this clinical study. These SAEs should also be reported promptly to the IEC/IRB that approved the study. All SAE reports should be transmitted to the IEC/IRB with a cover letter or transmittal form, and a copy of that transmittal should be maintained in the Investigator's files and forwarded to Alnylam as part of the TMF on study completion.

